4.3 STUDY TREATMENT AND OTHER TREATMENTS RELEVANT TO THE STUDY DESIGN

The IMP for this study is RO7496998 (AT-527) or matching placebo.

4.3.1 Study Treatment Formulation and Packaging

4.3.1.1 RO7496998 (AT-527) and Placebo

RO7496998 (AT-527) will be supplied by the Sponsor as 275 mg tablets in high-density polyethylene bottles with child-resistant closures. For information on the formulation and handling of RO7496998 (AT-527), see the pharmacy manual.

Placebo for RO7496998 (AT-527) will be supplied by the Sponsor as matching 275 mg tablets.

4.3.2 Study Treatment Dosage, Administration, and Compliance

The treatment regimens are summarized in Section [3.1](#).

Refer to the pharmacy manual for detailed instructions on drug preparation and administration.

Details regarding treatment administration (e.g., dose and timing) should be noted on the Study Drug Administration electronic Case Report Form (eCRF). Cases of overdose, medication error, drug abuse, or drug misuse, along with associated adverse events, should be reported as described in Section [5.3.5.11](#).

Guidelines for treatment interruption or discontinuation for patients who experience adverse events are provided in Section [5.1.2](#).

4.3.2.1 RO7496998 (AT-527) and Placebo

RO7496998 (AT-527) is provided as 275 mg tablets; two tablets will be administered orally BID from Day 1 to Day 5. Matching placebo is provided as 275 mg tablets; two tablets will be administered orally BID from Day 1 to Day 5.

RO7496998 (AT-527) (or matching placebo) should be taken orally at 12-hour intervals (± 2 hours). If the first study dose is taken prior to 2:00 p.m. on Day 1, the next dose should be taken in the evening of the same day (i.e., prior to midnight on the same calendar day with a minimum of 10 hours between doses). For these patients, the final (tenth) dose will be taken in the evening of Day 5. However, if the first study dose is taken after 2:00 p.m. on Day 1, the next dose should be taken in the morning of Day 2. For these patients, the final (tenth) dose will be taken on the morning of Day 6.

4.3.3 Rescue Medication

If COVID-19 symptoms, such as fever and headache, are so severe, in the opinion of the patient or investigator, that the patient needs rescue therapy between Day 1 and Day 29, the use of acetaminophen will be permitted only for the relief of severe symptoms. If acetaminophen is used, this should be recorded on the Concomitant Medications eCRF by the investigator, recording the dates and dosing at the next visit. Acetaminophen will not be provided by the Sponsor.

4.3.4 Investigational Medicinal Product Handling and Accountability

All IMPs required for completion of this study (RO7496998 [AT-527] or matching placebo formulations) will be provided by the Sponsor. The study site (i.e., investigator or other authorized personnel [e.g., pharmacist or mobile nurse]) is responsible for maintaining records of IMP delivery to the site, IMP inventory at the site, IMP use by each patient, and disposition or return of unused IMP, thus enabling reconciliation of all IMP received, and for ensuring that patients are provided with doses specified by the protocol.

The study site should follow all instructions included with each shipment of IMP. The study site will acknowledge receipt of IMPs supplied by the Sponsor, using the IxRS. Any damaged shipments will be replaced. The investigator or designee must confirm that appropriate temperature conditions have been maintained during transit, either by time monitoring (shipment arrival date and time) or temperature monitoring, for all IMPs received and that any discrepancies have been reported and resolved before use of the IMPs. All IMPs must be stored in a secure, environmentally controlled, and monitored (manual or automated) area in accordance with the labeled storage conditions, with access limited to the investigator and authorized staff.

Only patients enrolled in the study may receive IMPs, and only authorized staff may supply or administer IMPs.

IMPs will either be disposed of at the study site according to the study site's institutional standard operating procedure or be returned to the Sponsor with the appropriate documentation. The site's method of destroying Sponsor-supplied IMPs must be agreed to by the Sponsor. The site must obtain written authorization from the Sponsor before any Sponsor-supplied IMP is destroyed, and IMP destruction must be documented on the appropriate form.

Accurate records of all IMPs received at, dispensed from, returned to, and disposed of by the study site should be recorded on the drug accountability log.

Refer to the pharmacy manual and AT-527 Investigator's Brochure for information on IMP handling, including preparation and storage, and accountability.

4.3.5 Continued Access to RO7496998 (AT-527)

Currently, the Sponsor does not have any plans to provide Roche IMP (RO7496998 [AT-527]) or any other study treatments to patients who have completed the study. The Sponsor may evaluate whether to continue providing RO7496998 (AT-527) in accordance with the Roche Global Policy on Continued Access to Investigational Medicinal Product, available at the following website:

http://www.roche.com/policy_continued_access_to_investigational_medicines.pdf

4.4 CONCOMITANT THERAPY, PROHIBITED THERAPY, AND ADDITIONAL RESTRICTIONS

Concomitant therapy consists of any medication (e.g., prescription drugs, over-the-counter drugs, vaccines, herbal or homeopathic remedies, nutritional supplements) used by a patient in addition to protocol-mandated treatment from 7 days (12 months for COVID-19 vaccines) prior to initiation of study drug to the end of study visit. All such medications should be reported to the investigator and recorded on the Concomitant Medications eCRF.

4.4.1 Permitted Therapy

Patients are permitted to use the following therapies during the study:

- Hormonal contraceptives (see Section 4.1.1)
- Acetaminophen (*paracetamol*)
- Hormone replacement therapy
- Prescribed medications for concomitant conditions as per medical history, *such as antihypertensives, antidiabetic medications, rheumatologic medications or respiratory medications (e.g., chronic inhaled/intranasal/oral steroids)*
- Low dose aspirin
- COVID-19 vaccination (see Section 4.5.2 for documentation requirements pertaining to vaccine type and date of dosing).

Patients are not to be vaccinated during the first 2 weeks of the study.

Patients must have *at least* a 40-day window since their last dose of vaccination (second dose if applicable) prior to enrollment.

4.4.2 Cautionary Therapy

Concomitant use of herbal therapies is not recommended because their pharmacokinetics, safety profiles, and potential drug–drug interactions (*DDI*) are generally unknown.

In *in vitro* experiments, AT-511 (the free base form of RO7496998) demonstrated the potential for *the following DDIs* (see *Appendix 7* for more details):

Cytochrome P450 (CYP) 3A4 sensitive substrates

- CYP3A4 induction: weak induction at mRNA level with no increase in CYP3A4 enzyme activity. The clinical relevance (e.g., potential for decreased efficacy of oral contraceptives) of this finding has not been evaluated. As a precaution, hormonal contraceptive methods in women with childbearing potential must be supplemented by a barrier method (see Section 4.1.1).
- CYP3A4 inhibition: time-dependent and reversible inhibition by AT-511. CYP3A4 sensitive substrates, in particular, those with a narrow therapeutic index (NTI), should be used with caution. Common examples of CYP3A4 sensitive substrates with NTI include aminophylline, warfarin, methotrexate and amitriptyline. A list of CYP3A4 substrates with NTI is available at: <https://go.drugbank.com/categories/DBCAT004028>.

Consider substituting or stopping CYP3A4 substrates with NTI during *study* treatment and resume 2 days after the *final* dose. In the event that the CYP3A4 substrate with NTI cannot be safely discontinued or substituted, close monitoring is required.

P-glycoprotein (P-gp) sensitive substrates

- P-gp inhibition: staggered dosing can effectively mitigate potential for a clinical DDI at the level of the gastrointestinal tract. In the event that sensitive substrates of P-gp with a NTI cannot be safely discontinued or substituted, they should be dosed 2 hours after study drug administration, by which time absorption of AT-511 is considered essentially complete. Common examples of P-gp sensitive substrates with NTI include digoxin and tamoxifen.

For a list of sensitive P-gp substrates with NTI refer to <https://go.drugbank.com/categories/DBCAT004027>.

Breast Cancer Resistance Protein (BCRP) sensitive substrates

- BCRP inhibition: staggered dosing can effectively mitigate potential for a clinical DDI. In the event that sensitive substrates of BCRP with NTI cannot be safely discontinued or substituted, they should be dosed 2 hours after study drug administration. Common examples of BCRP sensitive substrates include ivermectin, pravastatin, rosuvastatin, apixaban and rivaroxaban.

For a list of sensitive BCRP substrates refer to <https://go.drugbank.com/categories/DBCAT002663>.

In *in vitro* experiments, the plasma circulating nucleoside metabolites AT-229 and AT-273 (inactive metabolites of AT-511) demonstrated potential for the following DDI (See [Appendix 7](#) for more details):

BCRP inhibitors or inducers

- BCRP inhibitors or inducers may affect plasma levels of AT-229. However, AT-229 is considered an inactive metabolite, and changes in AT-229 PK are not expected to affect the antiviral activity of AT-527. Consider substituting or stopping drugs that are major BCRP inhibitors or inducers during study treatment

and resume 12 hours after the final dose of study drug. In the event that the BCRP inhibitors or inducers cannot be safely discontinued or substituted, they should be used with caution. Common examples of BCRP inhibitors include omeprazole, lansoprazole and buprenorphine. Common examples of BCRP inducers include venlafaxine.

For a list of BCRP inhibitors and inducers, refer to <https://go.drugbank.com/categories/DBCAT002662> and <https://go.drugbank.com/categories/DBCAT003986>, respectively.

Organic Anion Transporter 1 and 3 (OAT1 and OAT3) inhibitors

- OAT1 and OAT3 inhibitors may affect plasma levels of AT-273. However, AT-273 is considered an inactive metabolite, and changes in AT-273 PK are not expected to affect the antiviral activity of AT-527. Consider stopping drugs that are major OAT1/3 inhibitors during study treatment and resume 12 hours after the final dose of study drug. In the event that the OAT1/3 inhibitors cannot be safely discontinued or substituted, they should be used with caution. Common examples of OAT1/3 inhibitors include furosemide, losartan and cimetidine.*

For a list of OAT1 and OAT3 inhibitors, refer to <https://go.drugbank.com/categories/DBCAT004041> and <https://go.drugbank.com/categories/DBCAT003946>, respectively.

4.4.3 Prohibited Therapy

Use of the following concomitant therapies is prohibited from Day 1 (unless otherwise specified below) until study completion or early termination, as described below:

- Investigational therapy (other than protocol-mandated study treatment)
- Treatment with a COVID-19 therapeutic agent including, but not limited to, other direct or indirect acting antivirals *against SARS-CoV-2 (such as remdesivir or favipiravir), systemic or inhaled steroids (such as dexamethasone or inhaled budesonide), colchicine, ivermectin, interferons, convalescent plasma, monoclonal antibodies against SARS-CoV-2 or IL-6, intravenous immunoglobulin or other EUA-approved treatments*
- Sofosbuvir, for patients with active HCV
- Abacavir for patients with HIV
- P-glycoprotein (P-gp) inhibitors hydroxychloroquine or amiodarone *within 3 months prior to screening and during the study*

Use of other P-gp inhibitors may be permitted in the event the P-gp inhibitor cannot be safely discontinued or substituted. If an appropriate substitute cannot be identified, dosing of *study drug* and the P-gp inhibitor must be staggered by 2 hours (with *study drug* dosed first). Patients may resume use of the substituted P-gp inhibitor approximately 12 hours after the final dose of *study drug*.

For a list of P-gp inhibitors, refer to <https://go.drugbank.com/categories/DBCAT002667>

Macrolides (including azithromycin) may be used if dosing is staggered as described above.

- P-gp inducers, including the following:
 - Anticonvulsants: carbamazepine, phenytoin, phenobarbital, oxcarbazepine
 - Rifamycins: rifabutin, rifampin, rifapentine
 - St. John's wort
 - HIV protease inhibitors (tipranavir/ritonavir)

For other P-gp inducers, *study drug* dosing cannot be initiated unless the investigator determines that the P-gp inducer can be safely discontinued or substituted. Patients may resume use of the substituted P-gp inducers approximately 12 hours after the final dose of *study drug*.

For a list of P-gp inducers, refer to
<https://go.drugbank.com/categories/DBCAT002666>

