There are now a number of vaccines with approvals or Emergency Use Authorizations (EUA) (or equivalent) for the prevention of SARS-CoV-2 infection. These remain in the early distribution phase and there are several logistical issues to be overcome in vaccinating large populations globally. Prevention and control of the disease remains a focus for public health measures to slow transmission, these include social distancing, the use of face masks, and national or regional lockdowns. Intravenous remdesivir, an inhibitor of RNA-dependent, RNA polymerase, and dexamethasone have shown benefit in hospitalized patients with COVID-19. However, in patients with moderate COVID-19, dexamethasone is not efficacious (and may be harmful), and use of remdesivir is not approved for non-hospitalized patients (Gandhi et al. 2020). There remains a significant and urgent unmet medical need for an orally administered direct acting antiviral drug with broad utility for the treatment of COVID-19. This will remain the case despite the availability of vaccinations, given that there will still be subsets of the population who will

refuse or not respond to the available vaccines, or individuals who have a contraindication and will need treatment options to be available. An antiviral therapeutic that could be administered to ambulatory, non-hospitalized patients has the potential to significantly reduce disease duration and deterioration of these patients, preventing progression of disease or hospitalization, and will have a significant impact on the pandemic and public health systems globally.

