1.3 STUDY RATIONALE AND BENEFIT-RISK ASSESSMENT

Despite the availability of vaccines, a need for treatment options with varying modes of action is still required. Currently available treatments (i.e., remdesivir and

dexamethasone) have demonstrated benefit only in hospitalized patients with COVID-19. Two virus-neutralizing monoclonal antibody cocktail therapies—bamlanivimab plus etesevimab, and casirivimab plus imdevimab—have been granted EUA for the treatment of mild to moderate COVID-19 in adults and pediatric patients (12 years and older weighing at least 40 kg) with positive results of direct SARS-CoV-2 viral testing and who are at high risk for progressing to severe COVID-19 and/or hospitalization. These monoclonal antibody interventions are administered intravenously, and therefore, present challenges in the outpatient setting. Alternative routes of administration such as orally administered COVID-19 treatments would be more practical for use in early disease. Eventually, it is likely multiple COVID-19 therapies will be required, both to address the medical needs of distinct patient populations and to bolster treatment supplies as caseloads continue to rise worldwide. Preventing hospitalizations and chronic sequelae of COVID-19 will not only save lives but also help restore healthcare systems and other institutions that are currently overburdened by the effects of the COVID-19.

Extensive nonclinical safety data, Phase I and Phase II clinical safety data in healthy volunteers and patients infected with HCV, favorable human PK data, and the potent in vitro antiviral activity of RO7496998 (AT-527) against SARS-CoV-2 replication, support further clinical evaluation of RO7496998 (AT-527) in patients with COVID-19. The main objective of the current study is to evaluate the efficacy and safety of RO7496998 (AT-527) in patients with mild or moderate COVID-19.

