3. STUDY DESIGN

3.1 DESCRIPTION OF THE STUDY

This is a Phase III, placebo-controlled, double-blind, multicenter study to assess the efficacy, safety, antiviral activity, and pharmacokinetics of RO7496998 (AT-527) compared with placebo in non-hospitalized adult and adolescent patients with mild to moderate COVID-19 in the outpatient setting.

The study will enroll approximately 1386 patients (including approximately 100 adolescents, up to a maximum of 150, with the remaining patients being adults) with confirmed SARS-CoV-2 infection. Patients will be randomized within 5 days of symptom onset. At the time of enrollment, patients must be stable as per eligibility criteria and not require hospitalization. Patients who, in the opinion of the treating physician are likely to experience imminent deterioration and require hospitalization will be excluded from the study. Patients confirmed to have other active viral or bacterial infections at the time of screening will be excluded.

Patients will be randomized as soon as possible after screening and within 48 hours. Patients who do not meet the criteria for participation in this study (screen failure) cannot be re-screened during the same illness episode. The investigator will record the reason for screen failure in the interactive voice or web-based response system (IxRS).

Eligible patients will be randomized on or prior to Day 1 in a 2:1 ratio to receive either RO7496998 (AT-527) or matching placebo. Patients will be orally administered 550 mg RO7496998 (AT-527) or matching placebo (two 275 mg tablets) BID for 5 days (see Section 4.3.2.1). Randomization will be stratified by geographic region (North America, Europe and rest of the world [ROW]) and presence of a high-risk factor (yes, no). A minimum of 40% of the overall study population will have a high-risk factor for hospitalization because of COVID-19. A minimum of 40% will also be expected for the otherwise healthy population. Patients may have ≥ 1 risk factor for hospitalization as a result of COVID-19 (see Section 3.3.2).

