4.5.6.3 Additional COVID-19 Related Assessments

Self-Reported Temperature

Patients will measure temperature four times a day between Days 1 and 5, BID between Days 6 and 10, and once daily between Days 11 and 29 (see [Appendix 3](#)).

COVID-19 Related Medically-Attended Visit(s) Assessment

A COVID-19-related medically-attended visit will be defined as follows: hospitalization, emergency room (ER) visit, urgent care visit, physician's office visit, or telemedicine visit, with the primary reason for the visit being COVID-19.

Only medically-attended visits related to COVID-19, as determined by the investigator, will be recorded in the eCRF. Details will include at minimum:

- Type of visit (hospitalization, ER, urgent care, physician's office visit, telemedicine)
- Date of visit
- Primary reason for COVID-19 related medically-attended visit
- Treatments given for COVID-19 (including, but not limited to, concomitant medications and supplemental oxygen)
- If hospitalization due to COVID-19 was required, include length of visit, whether ICU care was given, or whether mechanical ventilation was required

Any adverse events or concomitant therapies reported to the investigator should be recorded on the respective Adverse Events eCRF or Concomitant Medications eCRF.

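### Section 4.4.3 bans COVID-19 drugs, naming remdesivir and dexamethasone, to the end of the study, with no exception for a patient admitted with worsening COVID-19

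*Protocol*

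**What the plan says.** Protocol 4.4.3 opens its list with: "Use of the following concomitant therapies is prohibited from Day 1 (unless otherwise specified below) until study completion or early termination". One item is treatment with any COVID-19 therapeutic. Remdesivir is named among the antivirals and dexamethasone among the steroids. The section does write exceptions where they are wanted, but only for P-gp inhibitors (including macrolides) and P-gp inducers.

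Two neighbouring sections could have carried an exception and do not:

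- 4.3.3 (rescue): "the use of acetaminophen will be permitted only for the relief of severe symptoms".
- 4.4.1 (permitted therapy): steroids appear only among medicines for conditions in the medical history, as "respiratory medications (e.g., chronic inhaled/intranasal/oral steroids".

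On the value of the two drugs, 1.1 says that remdesivir and "dexamethasone have shown benefit in hospitalized patients with COVID-19", and 1.3 says that the available treatments "have demonstrated benefit only in hospitalized patients with COVID-19". Section 1.1 adds a limit: "in patients with moderate COVID-19, dexamethasone is not efficacious (and may be harmful), and use of remdesivir is not approved for non-hospitalized patients".

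Admission is foreseen. Section 3.1 says: "A minimum of 40% of the overall study population will have a high-risk factor for hospitalization because of COVID-19". COVID-19 hospitalization is a secondary endpoint, and 3.1 asks that visits continue to study end, where possible, for patients admitted during the treatment period.

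**The concern.** Remdesivir and dexamethasone are the two drugs the protocol itself singles out as helping hospitalized COVID-19 patients, and it forbids both by name until the patient completes or leaves the study. The ban makes sense in outpatients, where another active drug could blur the symptom comparison. That reason loses most of its force once a patient is in hospital with worsening disease.

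The first thing at stake is patient care: a site that follows the text would hold back treatment the protocol calls beneficial. The second is conduct. A site that treats the patient anyway, as most would, records ordinary inpatient care as a protocol deviation, or may conclude that the patient has to come off study. That would cost follow-up on the sickest patients, whom 3.1 wants kept.

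**Working it through.** The plan gives no figure to reproduce. The check is whether any section lifts the ban, and what a site could then do.

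**1. Scope and duration.** The ban runs from Day 1 to study completion (about Day 33) or early termination. Stopping study drug does not end it: under 4.6.1 and Appendix 1 footnote e, a patient who stops drug stays in the study and keeps being assessed.

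**2. Search for an exception.**
- 4.3.3: acetaminophen only.
- 4.4.1: chronic medication for existing conditions only.
- 4.4.3: exceptions for P-gp drugs and macrolides only.
- 4.6 (discontinuation), 5.3.5.9 (worsening) and 5.3.5.10 (hospitalization): none.
- 9.2 (deviations): deviations are documented and explained, but prospective requests to deviate are not allowed.
- SAP Table 2 and 5.6.6: analysis and summary rules, with no permission.

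**3. What a literal reader can do for an admitted patient.** Three courses remain:
- withhold the drugs, against the benefit stated in 1.1 and 1.3;
- give them and log a deviation, bearing in mind that 4.6.2 lists non-compliance with protocol requirements as a possible reason for discontinuation;
- end the patient's participation so that the ban lapses, against the follow-up instruction in 3.1 and footnote e.

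**4. Does the analysis need the ban after admission?** Protocol 6.4.1 ignores rescue and concomitant medication and keeps the observations that follow. SAP Table 2 applies treatment policy to the efficacy endpoints irrespective of such therapy, and its treatment note compares the arms whatever else is taken. The estimand is therefore defined with or without inpatient COVID-19 drugs.

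**5. Size.** The ban covers all 1386 planned patients but affects only those admitted with worsening disease. The documents give no admission rate, so one has to be assumed:
- 1%: 0.01 × 1386 = 13.9, about 14 patients;
- 6%: 0.06 × 1386 = 83.2, about 83 patients.

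The 40% high-risk minimum in 3.1 shows that admissions are expected. It does not give their number.

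**The case against.** The strongest reply is that sites will treat the patient regardless. No section tells them to withhold inpatient care, 8.1 applies whichever standard better protects the individual, and 9.2 lets a deviation be documented and explained. All of this stands, and it means the literal harm is unlikely to be common. It does not tell a site that 4.4.3 is lifted, and it leaves foreseeable care classed as a deviation.

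A reader might infer that the plan contradicts itself because other sections expect and accept inpatient COVID-19 drugs. The documents do not go that far. The item in 4.5.6.3, "Treatments given for COVID-19 (including, but not limited to, concomitant medications and supplemental oxygen", applies to every COVID-19 visit, including office and telemedicine visits, where the ban is meant to hold. SAP 5.6.6 summarizes any treatment given for COVID-19, which can include permitted acetaminophen. A plan may also prohibit a drug and still analyze data collected after its use. These passages show that the ban is not needed for the analysis; they do not grant permission.

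A reader might also infer that dexamethasone helps every admitted patient. The caveat in 1.1 turns on severity, not on setting, and 1.2 describes a trial in hospitalized patients with moderate COVID-19. This stands, and it is why an exception should leave the choice to the treating physician.

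Finally, 1.1 describes remdesivir as inhibiting the viral RNA polymerase, and 1.2 gives study drug the same target. Admission could fall within the dosing days, and 5.1.2.2 does not allow interruption. An exception therefore has to say what happens to the remaining doses.

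**Conclusion.** The concern holds as a gap in a stated rule. Section 4.4.3 has no exception for patients hospitalized with worsening COVID-19, and followed to the letter it gives a result at odds with 1.1, 1.3 and 3.1. It should be fixed because it touches patient care and the remedy is cheap.

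The documents do not support a stronger conclusion. They do not show that patients will be denied care, or that any outcome will be lost: withdrawal is discretionary, and 5.3.5.7 requires deaths within the reporting period to be recorded. The primary endpoint is little affected. The ban remains sound for non-hospitalized patients.

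The size, about 14 to 83 patients, rests wholly on the assumed 1% to 6% admission rate. The textual finding rests on no assumption beyond reading 4.4.3 as written.

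**What to change.** Add to protocol 4.4.3:

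*Patients hospitalized for worsening COVID-19 (not for isolation only) may receive standard-of-care COVID-19 treatment as judged by the treating physician; any remaining study drug is continued or permanently stopped at the investigator's judgment under 4.6.1; the treatment is recorded, is not a protocol deviation, and is not a reason to withdraw the patient from the study.*

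Keep the ban unchanged for non-hospitalized patients. The words on isolation keep it in force for the policy admissions described in 5.3.5.10.

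The cost is one sentence and a note to sites. No visits, patients or data fields are added, since 4.5.6.3 already collects the treatments. The downside is somewhat more use of other active drugs after admission, which the treatment-policy estimand already accommodates.
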